The DLT evaluation period will be at least 28 days for all cohorts. The DLT evaluation period may also be extended to assess events starting within the DLT window. Any adverse event occurring outside the DLT window that meets the DLT definition and is determined by the investigator to be possibly related to AMG 562, and seen more frequently, or is more severe than expected, or is persistent despite appropriate management, can be determined to be a DLT upon unanimous decision by the DLRT after review of the event and all available safety data. A DLRM will be conducted after the subjects in each dose cohort have had the opportunity to complete the DLT evaluation period. The DLRT may also convene at any time to review safety data if deemed necessary.

Subjects who complete the DLT period may proceed to a higher dose level for the next dosing (intra-subject dose escalation) once this higher dose level has been deemed safe by the DLRT and after consultation with the Amgen Medical Monitor if:

- no DLT has been reported for this subject during or after completion of the DLT period
- the subject has not experienced any grade ≥ 2 adverse events (deemed treatment related by the investigator) during treatment

DLTs experienced by subjects after completing the DLT period will be considered in the BLRM design to account for any late onset toxicity.

Dose exploration will continue until any of the following events:

The highest planned dose level is determined to be safe and tolerable (minimum of 6 treated subjects)

- An MTD is identified where BLRM repeats the recommendation of a dose level (minimum of 6 treated subjects)
- If fewer than 6 subjects are treated at the MTD/RP2D, additional subjects may be enrolled to confirm safety and tolerability.

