Dose escalation/de-escalation recommendations will be guided by the BLRM model of dose toxicity and evaluation of all available safety data, laboratory, and PK information. If two or more subjects experience a DLT at a dose level, enrollment to the cohort will be terminated and dose de-escalation may occur. If late onset adverse events occur during a cohort, the DLRT may adaptively re-consider the doses evaluated within a cohort for subsequent dosing and/or possibly trigger a de-escalation or withholding of additional doses in subsequent cohorts. Based on the BLRM model and after reviewing all available safety and tolerability data, the DLRT will make dose escalation/de-escalation recommendations. Subjects may continue to receive AMG 562 until evidence of disease progression, unacceptable toxicity or withdrawal of consent.

In addition to the dose, the DLRT may recommend changing the dosing schedule (eg, dosing interval) for subsequent cohorts. The DLRT may also recommend to prolong the DLT window or to include step-up dosing for future cohorts based on observed tolerability and other clinical signs, pharmacological and PD results.

Dose exploration will be conducted in 2 stages using the BLRM design to guide dose escalation. In the initial cohorts, single subjects will be enrolled at dose levels anticipated to be lower than the dose levels at which adverse events related to AMG 562 may be observed. Once higher dose levels are open for enrollment or any of the safety criteria listed below are observed, multiple subject cohorts of 3 to 4 subjects per cohort will open for enrollment. Enrollment of subjects at each dose level in the multiple subject cohorts will be staggered by at least 3 days.

The switch from single to multiple subject cohorts will be triggered if at least one subject experiences any of the three safety events below (whichever occurs earlier):

- 1. Non hematologic adverse event grade  $\geq 2$
- 2. Hematologic adverse event grade ≥ 3 including anemia, neutropenia, leukopenia, thrombocytopenia, and lymphopenia
- 3. DLT

Once a subject experiences a DLT, the dose for the subsequent cohorts will be decided by the DLRT after evaluating all available safety, laboratory, and PK data as well as the recommendation from the BLRM. The dose escalation for subsequent cohorts will be limited to 2-fold increases or lower after a subject experiences a DLT or  $\geq$  2 patients experience a grade  $\geq$  2 adverse event.

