The DLT evaluation period will be 28 days for all cohorts. The DLT evaluation period may also be extended to assess events starting within the DLT window in case the DLT definition is time dependent. Any adverse event occurring outside the DLT window that meets the DLT definition and is determined by the investigator to be possibly related to AMG 562, and is seen more frequently, or is more severe than expected, or is persistent despite appropriate management, can be determined to be a DLT upon unanimous decision by the DLRT after review of the event and all available safety data. A DLRM will be conducted after the subjects in each dose cohort have had the opportunity to complete the DLT evaluation period. The DLRT may also convene at any time to review safety data if deemed necessary.

Subjects who complete the DLT period may proceed to a higher dose level for the next dosing (intra-subject dose escalation) once this higher dose level has been deemed safe by the DLRT and after consultation with the Amgen Medical Monitor if:

- no DLT has been reported for this subject during or after completion of the DLT period
- the subject has not experienced any ≥ grade 2 adverse events (deemed treatment related by the investigator) during treatment

DLTs experienced by subjects after completing the DLT period will be considered in the BLRM design to account for any late onset toxicity.

Premedication for Cycle 1: an 8 mg dose of IV or PO dexamethasone approximately 1 hour prior to the start of the AMG 562 infusion is mandatory:

• Prior to each infusion in Cycle 1 8 mg dexamethasone IV or PO as premedication

Premedication for Cycle 2 and beyond:

o Pre medication with 8 mg IV or PO dexamethasone for each subsequent cycle will be required for any subject who experienced grade ≥ 2 neurotoxicity or grade ≥ 2 CRS in the preceding cycle

If CRS and neurotoxicity of grade 2 or higher did not occur in the prior cycle(s), premedication with dexamethasone can be reduced to 4 mg. If subjects tolerate AMG 562 well with reduced dose dexamethasone, premedication with dexamethasone can be discontinued for the next cycle in consultation with Amgen Medial Monitor

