#### 6.2.1.3 Dose Limiting Toxicities (DLTs)

The DLT window (ie, DLT evaluable period) will start on Day 1 (start of the administration of the first infusion). The duration of the DLT window is 28 days from infusion Day 1.

The DLT window may also be extended to assess events starting within the window in case the DLT definition is time dependent.

See Section 3.4 for description of DLT evaluability and replacement of subjects.

All available safety data for subjects who are not DLT evaluable will still be evaluated and considered in DLRT recommendations.

A DLT will be defined as any of the events described below occurring in a subject during the DLT window unless clearly attributable to causes other than AMG 562 treatment. The CTCAE version 4.0 (see Appendix A) will be used to assess toxicities/adverse

events with the exception of CRS and tumor lysis syndrome (TLS). See Section 6.2.1.4 and Appendix K for grading criteria of CRS, neurotoxicity and TLS respectively.

- 1. Death not clearly due to the underlying disease or extraneous causes.
- 2. Any subject meeting the criteria for Hy's Law case (ie, severe drug-induced liver injury [DILI]) will be considered a DLT. A Hy's Law case is defined as: AST or ALT values of ≥ 3x ULN AND with serum total bilirubin (TBIL) level of > 2x ULN or INR > 1.5 without signs of cholestasis and with no other clear alternative reason to explain the observed liver-related laboratory abnormalities (see Section 6.4 for hepatotoxicity management and Appendix A for further explanation of Hy's law case and Management of Hepatic Function)
- 3. Non-hematologic DLTs:
  - Non-hematological adverse event grade 3 or higher, EXCEPT:
    - infection responding to antibiotic/anti-infective treatment within 48 hours
    - grade 3 fatigue or asthenia
    - grade 3 headache that improves to grade ≤ 2 within 72 hours
    - grade 3 insomnia that improves to grade  $\leq$  2 within 72 hours
    - grade 3 fever that improves to grade  $\leq$  2 within 72 hours
    - grade 3 nausea, vomiting or diarrhea responding if managed with optimal medical support and resolves within 72 hours
    - laboratory parameters of grade ≥ 3, not considered clinically relevant , and improved to grade ≤ 2 within 72 hours
- 4. Hematologic DLTs:
  - Febrile neutropenia grade 3 or higher unless responding to antibiotic/anti-infective treatment within 48 hours
  - Grade 4 neutropenia lasting more than 5 days
  - Grade 4 thrombocytopenia lasting more than 7 days

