  - Grade 3 thrombocytopenia with hemorrhage or required platelet transfusion
  - Grade 3 anemia with symptoms or required intervention (eg, transfusion)
  - Grade 4 anemia in the absence of detectable lymphoma as it may reflect a marrow toxic effect of AMG 562

Any adverse event, that meets the DLT definition, occurring outside the DLT evaluation period that is determined by the investigator to be possibly related to AMG 562, which is seen more frequently or is more severe than expected or is persistent despite appropriate management, can be determined to be a DLT upon unanimous decision by the DLRT after review of the adverse event and all available safety data.

An event should be considered related to treatment if, in the investigator's medical judgement, there is a reasonable possibility that the event may have been caused by AMG 562.

The dosing schedule is described by Part 1 Study Design and Schema and also in the protocol synopsis.

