### 10.4.2 Dose Level Review Team (DLRT)

Dose Level Review Meetings (DLRMs) will be held to review data, monitor safety, and make recommendations on dose escalation or / changes. The DLRT will be composed of the investigators or designees, and the following Amgen representatives: Medical Monitor/early development leader or designee, global safety officer or designee, clinical study manager, biostatistician and clinical pharmacologist. Additional members may be added as needed. The following members are responsible for DLRT recommendations: treating investigators, Amgen Medical Monitor, and global safety officer or designee before rendering final decision by Amgen.

A quorum as defined below must be in attendance for the DLRM. The quorum is defined as > 50% of the participating investigators or their qualified designee (ie, sub-investigator or research nurse or study coordinator possessing written documentation [eg e-mail] of the investigator's vote), as well as > 50% of Amgen representatives listed above. The

early development leader/medical monitor must attend for the quorum to be reached. The DLRM will be rescheduled if a quorum is not reached.

All available study data, including data collected after the initial DLT window, and including demographics, IP administration, medical history, concomitant medications, adverse events, ECGs, vital signs, laboratory data, efficacy and PK/PD information will be reviewed. In addition to DLTs, all ≥ grade 3 toxicities not meeting DLT criteria will be reviewed and may be considered in DLRT recommendations.

All DLRM requirements are outlined in the protocol. A DLRM Charter will not be used.

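### Under step-up dosing, neither DLT evaluability nor the 28-day DLT window is tied to the target dose that the BLRM models

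*Protocol*

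**What the plan says.** Protocol Section 6.2.1.3 starts the DLT window at the first infusion: "The duration of the DLT window is 28 days from infusion Day 1". Section 3.1 (Part 1: Dose Exploration) agrees: "The DLT evaluation period will be 28 days for all cohorts". The synopsis makes 28 days a floor: "The DLT evaluation period will be at least 28 days for all cohorts". SAP Section 5 uses the same floor. None of these counts from the first target dose.

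Section 3.1 (Step-up Dosing) allows up to three intermediate doses before the target dose and lets the DLRT lengthen the step interval from one day to two, three or four. After a DLT on the step, the BLRM estimates the target dose. The model in Appendix J has a dose term and no follow-up term.

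Section 3.4 decides evaluability by counting missed doses out of four planned. Subjects who stop early for a reason other than a DLT are not evaluable, with one exception: early progression after three or more doses of study drug, with safety follow-up over the whole window. Neither rule mentions the target dose. The DLT analysis set (Protocol Section 10.1.2, SAP Section 6.4) adds no such condition.

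There are safeguards:
- The data review in Section 10.4.2 covers "All available study data, including data collected after the initial DLT window", and that review is compulsory.
- Section 3.1 says "The DLRT may also recommend to prolong the DLT window or to include step-up dosing for future cohorts", and lets the DLRT reconsider doses after late-onset events.
- An out-of-window event that meets further conditions "can be determined to be a DLT upon unanimous decision by the DLRT".
- "DLTs experienced by subjects after completing the DLT period will be considered in the BLRM design to account for any late onset toxicity".
- SAP Section 9.6.1 provides a listing of out-of-window DLTs.

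**The concern.** The BLRM treats each evaluable subject as one observation at the modelled dose. That is fair if every such subject received the dose and was watched for a similar time on it. Two rules can break this under step-up dosing.

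The first is evaluability. A subject given only run-in doses carries no information about the target dose. Counted as evaluable without a DLT, that subject lowers the estimated DLT rate at a dose never received.

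The second is time at the target dose. The dose review is tied to the window: "A DLRM will be conducted after the subjects in each dose cohort have had the opportunity to complete the DLT evaluation period". If the target dose comes late, the review rests on fewer days and fewer target doses. A later DLT can enter the model afterwards, but was not available for that recommendation. Both effects lean towards escalation, and Section 3.1 doubles the step dose until a DLT is seen.

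Elsewhere the protocol does count from the target dose: step-up hospitalisation (Section 6.2.1.1), intensive PK sampling (Table 9 footnotes) and the timing of the expansion analysis (Section 3.5.2). Later toxicity is also plausible. The predicted half-life is about 16 days (Section 2.2.2), accumulation was seen in monkeys (Section 2.2.3), and DLTs include prolonged cytopenias and Hy's Law cases as well as CRS.

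**Working it through.** **The plan's own figure.** Section 10.2 gives a 27-70% chance of at least one DLT in 3 subjects, and 34-80% in 4, at true rates of 10-33%. With 1 − (1 − p)^n:
- n = 3: 1 − 0.90³ = 27.1%; 1 − 0.67³ = 69.9%
- n = 4: 1 − 0.90⁴ = 34.4%; 1 − 0.67⁴ = 79.8%

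The stated figures reproduce.

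**Table 12, row by row.** For a first target dose on day t, days left in the default window = 29 − t, counting the dosing day, so that flat dosing gives 28. As elapsed days to Day 28, the values for Days 9, 10 and 17 are 19, 18 and 11.

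| Intermediate doses, interval | Infusions by Day 28 | Run-in / target | First target | Days left | Target doses among first three |
|---|---|---|---|---|---|
| none, 48 h | 5 | 1 / 4 | Day 3 | 26 | 2 |
| none, 72 h | 5 | 1 / 4 | Day 4 | 25 | 2 |
| one, 48 h | 6 | 2 / 4 | Day 5 | 24 | 1 |
| one, 96 h | 5 | 2 / 3 | Day 9 | 20 | 1 |
| two, 72 h | 6 | 3 / 3 | Day 10 | 19 | 0 |
| three, 48 h | 7 | 4 / 3 | Day 9 | 20 | 0 |
| three, 96 h | 6 | 4 / 2 | Day 17 | 12 | 0 |

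Every row has 5 to 7 infusions, so Section 3.4's count of four fits none of them.

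**Evaluability.** In the last three rows the first three doses are all run-in. The gap between the third dose and the first target dose is Day 7 to 10, Day 5 to 9, and Day 9 to 17. A subject who stops for progression in that gap, with follow-up completed, meets the exception. The same holds for two or three intermediate doses at one-day steps, where the gap is shorter. If it happened once in a cohort of four, three subjects would be informative: 1 − 0.67³ = 69.9% instead of 79.8%. This is the size per occurrence; the documents give no basis for its frequency.

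**Window.** Let f be the assumed share of the 28-day cumulative hazard falling at the first target dose, with the rest spread evenly over 28 days. The rate seen is s = 1 − 0.67^(f + (1 − f)(29 − t)/28), and the chance of at least one DLT in four is 1 − (1 − s)⁴. This counts target-dose DLTs only and assumes that no post-window event is voted a DLT. Cells show the rate seen, then the chance in four.

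| First target | f = 0 | f = 0.5 | f = 0.8 | f = 1 |
|---|---|---|---|---|
| Day 9 | 24.9%; 68.2% | 29.1%; 74.7% | 31.4%; 77.9% | 33.0%; 79.8% |
| Day 10 | 23.8%; 66.3% | 28.5%; 73.9% | 31.3%; 77.7% | 33.0%; 79.8% |
| Day 17 | 15.8%; 49.7% | 24.9%; 68.2% | 29.9%; 75.8% | 33.0%; 79.8% |

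For example, Day 17 with f = 0.8: the exponent is 0.8 + 0.2 × 12/28 = 0.886, and 1 − 0.67^0.886 = 29.9%. For a Day 5 target the rates seen are 29%, 31%, 32% and 33%, so early targets lose little.

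**The case against.** The strongest reply is that step-up dosing exists to blunt first-dose effects (CRS, neurologic events, tumor lysis syndrome), and Section 6.2.1.4.2.6 puts the raised CRS risk in the first few days after infusion. Such events would fall inside even a 12-day remainder. A reader might infer from the table that a late target halves the visible DLT rate. The documents do not support that: the 15.8% needs constant hazard, which fits poorly with this rationale. The objection stands as to size, but not for later-onset DLTs.

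Second, the safeguards are real. It would be wrong to say that post-window data are ignored or that every safeguard is optional. Review of those data is compulsory, the DLRT may meet at any time, and it may revisit doses after late events. What remains is that nothing lengthens the window when the target is late, and that a late event becomes a DLT only by unanimous decision.

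Third, a reader might infer that three run-in doses alone make a subject evaluable. They do not. Early progression and safety follow-up over the whole window are also required, in a gap of a few days, in subjects with an expected survival of at least 12 weeks and no scheduled response assessment before week 5. The case is rare, but the rule still classifies it wrongly.

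Fourth, late targets are optional. The default step-up target is on Day 2, and the DLRT that lengthens the steps can also lengthen the window. That is fair, but the link is left to discretion.

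**Conclusion.** The point holds as a gap in the rules of limited size. The evaluability rule is the firmer part: as written it can place a subject who never received the modelled dose in the DLT set as a non-event. The window matters only for first target doses on Day 9 or later. There the rate seen for a true 33% ranges from no loss (all hazard at the first target dose), through about 30% for Day 17 with an 80% share, to 15.8% for Day 17 under constant hazard. The onset shares are assumptions, and run-in DLTs and post-window events voted as DLTs are left out. The last-enrolled subject has the fewest days; earlier subjects have more because enrolment is staggered by at least three days.

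A reader might also infer that the trial's reported DLT results are biased. The documents do not show that a late-target schedule was used. The SAP says that the study was discontinued early and that DLT probabilities will not be summarised (SAP Section 10). The DLT analysis set and DLT incidence remain open to the effect. The Part 1 schema and the step-up figures are not in the available text, so a rule stated only there could not be checked.

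**What to change.** **Evaluability (Protocol Section 3.4, SAP Section 6.4).** For step-up cohorts, count target doses. A subject is non-evaluable if two consecutive target doses are missed for a reason other than a DLT, and the early-progression exception requires at least three target doses. A DLT at any dose level still counts. For the remaining reporting, the condition can be applied to the SAP's DLT set. Cost: wording, and occasional replacement of early progressors.

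**Window (Protocol Sections 3.1 and 6.2.1.3, SAP Section 5).** Where the first target dose falls on Day 9 or later, run the window from Day 1 through 28 days from that dose, counting the dosing day. The end is t + 27: Day 36, 37 or 44 for a Day 9, 10 or 17 target. Cost: 8, 9 or 16 more days before dose review in those cohorts only, and total observation that differs between cohorts. Extending the window for Day 2 to 5 targets would gain almost nothing. On the Day 17 schedule the two changes go together, because only two target doses fall within the present window.

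**Clean-up.** Section 6.2.1.4.2.3 makes a subject in a single-subject cohort non-evaluable after one missed dose, while Section 3.4 requires two consecutive misses. Align the two. This has little remaining reach, since those cohorts are the lowest doses.
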